3.3 Apheresis Related Parameter Calculations

Parent container:

$$\text{Platelet Volume (mL)} = \frac{\text{Dual Bag Platelet Plus Product Weight (g)} - \text{Dual Bag Tare Weight(g)}}{1.03 \left(\frac{\text{g}}{\text{mL}}\right)}$$

$$\text{Plasma Volume (mL)} = \frac{\text{Plasma Bag Weight (g)} - \text{Plasma Bag Tare Weight(g)}}{1.03 \left(\frac{\text{g}}{\text{mL}}\right)}$$

$$\text{Average Platelet Concentration (x10}^3/\mu\text{L)} = \frac{1^{\text{st}} \text{ CBC (x10}^3/\mu\text{L)} + 2^{\text{nd}} \text{ CBC (x10}^3/\mu\text{L)}}{2}$$

$$\text{Platelet Yield (x10}^{11}\text{)} = \frac{[\text{Average Platelet Concentration}] * [\text{Dilution Factor}] * [\text{Platelet Volume}]}{100,000}$$

$$\text{Residual WBC Count (x10}^6\text{)} = \frac{[\text{Raw WBC Count (cells}/\mu\text{L)}] * [\text{Platelet Volume}]}{1,000}$$

Individual components (Products A, B, and C, where applicable, from the eCRFs):

$$\text{Platelet Volume (mL)} = \frac{\text{Bag Platelet Plus Product Weight (g)} - \text{Bag Tare Weight(g)}}{1.03 \left(\frac{\text{g}}{\text{mL}}\right)}$$

$$\text{Residual WBC Count (x10}^6\text{)} = \frac{[\text{Raw WBC Count (cells}/\mu\text{L)}] * [\text{Platelet Volume}]}{1,000}$$

3.4 Primary Endpoints

- Proportion of platelet units with an acceptable residual WBC level for single platelet products.
- Proportion of platelet units with an acceptable residual WBC level for double platelet products.
- Proportion of platelet units with an acceptable residual WBC level for triple platelet products.

The acceptable residual WBC level is defined as following:

For single platelet products: residual white blood cell measurement, rounded to the nearest tenth, $< 5.0 \times 10^6$.

For double platelet products:

- Parent container has a residual white blood cell measurement, rounded to the nearest tenth, $< 8.0 \times 10^6$,
- If not met, each component residual white blood cell measurement, rounded to the nearest tenth, $< 5.0 \times 10^6$.

For triple platelet products:

- Parent container has a residual white blood cell measurement, rounded to the nearest tenth, $< 12.0 \times 10^6$,
- If not met, each component residual white blood cell measurement, rounded to the nearest tenth, $< 5.0 \times 10^6$.

3.5 Secondary Endpoints

- Proportion of platelet units with an acceptable platelet yield for single platelet products.
- Proportion of platelet units with an acceptable platelet yield for double platelet products.
- Proportion of platelet units with an acceptable platelet yield for triple platelet products.

Acceptable platelet yield is defined as following, where the platelet yield is calculated from the formula in Section 3.3:

For single platelet products: platelet yield, rounded to the nearest tenth, $\geq 3.0 \times 10^{11}$.

For double platelet products: platelet yield, rounded to the nearest tenth, $\geq 6.2 \times 10^{11}$.

For triple platelet products: platelet yield, rounded to the nearest tenth, $\geq 9.3 \times 10^{11}$.

3.6 Safety Endpoints

Safety will be monitored through collection of adverse events (AEs), serious adverse events (SAEs), unanticipated adverse device effects (UADEs), and device deficiencies.

3.7 Statistical Analysis

All data collected on the eCRFs will be presented in the listings. Missing data will not be imputed. All analyses will be based on observed data only.

3.7.1 Demographic and Baseline Characteristics

Demographic and baseline characteristics will be summarized by platelet products (single, double, triple, and unassigned) and overall. Categorical variables (such as gender and race) will be summarized by frequency and percentage. Continuous variables (such as weight and height) will be summarized by N (number of non-missing observations), mean, standard deviation, median, minimum, and maximum.

3.7.2 Disposition

Study completion status and reasons for discontinuation will be displayed by platelet products (single, double, triple, and unassigned) and overall using frequencies and percentages.

3.7.3 Efficiency Analysis

Primary Endpoints

Primary Endpoint Acceptance Criteria

| Parameter | Measured | Acceptance Criteria |
|----------------------------------|--|--|
| Residual WBC Count – Single Unit | Flow cytometry; BD Leukocount™ or equivalent | Residual WBC count is $< 5.0 \times 10^6$ |
| Residual WBC Count – Double Unit | Flow cytometry; BD Leukocount or equivalent | Residual WBC count is $< 8.0 \times 10^6$ or each component $< 5.0 \times 10^6$ |
| Residual WBC Count – Triple Unit | Flow cytometry; BD Leukocount or equivalent | Residual WBC count is $< 12.0 \times 10^6$ or each component $< 5.0 \times 10^6$ |

Abbreviations: WBC = white blood cell.

Summary statistics will be provided separately for single, double, and triple residual WBC levels. The summaries will include N, mean, standard deviation, median, minimum, and maximum.

Frequencies and percentages of platelet units with an acceptable residual WBC level and the lower one-sided 95% exact binomial confidence intervals (Clopper-Pearson) will be calculated separately for single, double, and triple platelet products. If the lower one-sided confidence interval is greater than 95%, then it will be concluded that the

proportion of platelet units with an acceptable residual WBC level is at least 95% for the given platelet product.

Secondary Endpoints

Secondary Endpoint Acceptance Criteria

| Parameter | Measured | Acceptance Criteria ^a |
|------------------------------|---------------------------------|---|
| Platelet yield – Single Unit | Platelet concentration × volume | Platelet yield is $\geq 3.0 \times 10^{11}$ |
| Platelet yield – Double Unit | Platelet concentration × volume | Platelet yield is $\geq 6.2 \times 10^{11}$ |
| Platelet yield – Triple Unit | Platelet concentration × volume | Platelet yield is $\geq 9.3 \times 10^{11}$ |

^a These yields represent typical lab minimums for splitting into double and triple platelet products.

Platelet yield will be summarized separately for single, double, and triple platelet products. The summaries will include N, mean, standard deviation, median, minimum, and maximum.

Separately for single, double, and triple platelet products, the lower one-sided 95% exact binomial confidence intervals (Clopper-Pearson) will be calculated for the proportion of platelet units with an acceptable platelet yield. If the lower one-sided confidence interval is greater than 75%, then it will be concluded that the proportion of platelet units with an acceptable platelet yield is at least 75% for the given platelet product.

3.7.4 Calculated Apheresis Related Parameters

The average platelet concentration, platelet yield, and residual WBC count as specified in Section 3.3 will be summarized by N, mean, standard deviation, median, minimum, and maximum for each platelet product type.

3.7.5 Safety Analysis

All adverse events will be coded using MedDRA and reported by SOC and preferred term. The focus of the adverse event summaries will be on treatment-emergent adverse events. Adverse events will be considered treatment-emergent if they occur on or after the start of the apheresis procedure, as defined in Section 3.2. Adverse events (AEs), serious adverse events (SAEs), and unanticipated adverse device effects (UADEs) will be summarized with frequencies and percentages. Additional summaries of AEs will be presented for the maximum reported severity and relationship to device and procedure. AEs leading to study or procedure discontinuation will also be tabulated. Summaries will be presented by platelet products (single, double, triple, and unassigned) and overall.

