### **9.4 Enrollment**

A donor is considered to be an enrolled subject following informed consent. It is expected that, due to the screening and eligibility requirements, some fraction of subjects will not qualify for a platelet/plasma donation after consent and some who are enrolled may not complete their anticipated procedures. Subjects will be considered screen failures if they fail to meet any of the eligibility criteria, and subjects who do not complete their anticipated procedure (after venipuncture) will be considered as an early termination.

After informed consent has been obtained, subjects will receive a unique study identification number (USID). The USID number will use the following convention: 60XX-YYY, where XX is the pre-assigned site number and -YYY will be a sequential number starting with 001. The USID number will be recorded on the electronic Case Report Form (eCRF).

Subjects that fail screening criteria on information or laboratory values that are anticipated to change, may be rescreened. Subjects that have incomplete procedures or donated a product that meets any of the protocol analysis exclusions (Section 15.4) may rescreen if they meet all

inclusion criteria when they return. Subjects that are rescreened will be assigned a new USID number.

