#### **10.2.2 Apheresis Procedure**

Plateletpheresis will be per site standard practice and per applicable FDA guidelines such as the “Guidance for Industry and FDA Review Staff: Collection of Platelets by Automated Methods, December 2007” and the “Guidance for Industry: Pre-Storage Leukocyte Reduction of Whole Blood and Blood Components Intended for Transfusion, September 2012”.

Apheresis procedures will be run according to the instructions and precautions described in the Version 6.0 Trima Accel Operator’s Manual and the Version 7.0 user change summary.

The following procedures will be performed:

1. Venipuncture.
2. Collect venous whole blood sample.
  - a. Complete blood count (hemoglobin or hematocrit and platelet count).
3. Update Trima Accel device with updated platelet count and hemoglobin or hematocrit.

4. Perform apheresis procedure.
5. Record the following:
  - a. Type of cuff used.
  - b. Trima procedure details.
  - c. AEs, SAEs and UADEs.
  - d. Medical interventions to treat AEs, if applicable.
  - e. Device deficiencies.

This will conclude the subject's participation.

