## **13 ADVERSE EVENTS/EFFECTS**

### **13.1 Anticipated Risks**

#### **13.1.1 Potential Apheresis Related Risks**

Donor reactions are mostly transient self-limited events, and in very rare exceptions a donor may experience long-term morbidity or sustain permanent impairment. Small hematomas, presyncopal episodes, and citrate reactions account for the majority of complications in automated collection procedures, and younger or first-time donors are more likely to experience complications. Although rare (< 5 out of 10,000 apheresis donations), almost 40% of reactions requiring medical care outside the donation premises are venipuncture related, including large hematoma, and possible nerve irritation.

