### **15.2.3 Safety Measures**

Adverse events will be summarized by the medical dictionary for regulatory activities (MedDRA Version 18.1 or later). Tables will describe the frequency and percentage of all AEs, SAEs, and UADEs reported by subjects in the safety population. Presentations will summarize AEs by maximum reported severity and relationship to device and procedure. AEs leading to study or procedure discontinuation will also be tabulated.

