3.2 Study Populations

Analysis populations for this clinical investigation will be the Full Analysis Set (FAS) and Safety Populations.

For all analyses by platelet product, the platelet product type (single, double, triple, or unassigned) will be determined from the calculated platelet yield (see Section 3.3) using the following.

- If the platelet yield, rounded to the nearest tenth, is $\geq 9.3 \times 10^{11}$, then the product will be analyzed as a triple.
- Otherwise, if the platelet yield, rounded to the nearest tenth, is $\geq 6.2 \times 10^{11}$, then the product will be analyzed as a double.
- Otherwise, if the platelet yield, rounded to the nearest tenth, is $< 6.2 \times 10^{11}$, then the product will be analyzed as a single.
- Otherwise, if the procedure was not started, not completed or the platelet yield could not be determined for some other reason, as per the protocol analysis exclusion criteria, then the subject will be analyzed as “Unassigned”.

The Safety Population will include all subjects enrolled in this trial for whom at least 1 apheresis procedure is initiated. A procedure will be considered to have been initiated if a Trima procedure start date and time are present. The Safety Population will be used for all summaries except the primary and secondary endpoints and the derived apheresis related parameters.

Due to the design of the study, a given subject may be enrolled in the study on multiple occasions. These subjects may also qualify for the Safety Population more than once. If this occurs, the subjects will be analyzed separately for each enrollment.

The Full Analysis Set (FAS) will be defined separately for single, double, and triple platelet products and will not include any repeat subjects. The FAS for a given platelet product will consist of all collections that do not meet any of the exclusion criteria specified below. The FAS will be used to examine the primary and secondary endpoints and the derived apheresis related parameters.

Data points will be excluded from the FAS analysis in the following situations:

1. Inability to collect a complete unit due to:
 - a. Subject issues (inadequate access, reaction, needle abort, procedure disqualification upon Trima Accel device update of subject platelet count and hemoglobin or hematocrit).
 - b. Decision to stop procedure by subject, Investigator, nursing staff or operator.

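### Could adverse events at needle placement drop out of the safety tables because the SAP opens its treatment-emergent window at the Trima start time?

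*SAP*

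**What the plan says.** Protocol 15.2.3 makes a broad commitment: "Tables will describe the frequency and percentage of all AEs, SAEs, and UADEs reported by subjects in the safety population". It sets no treatment-emergent limit, and Protocol 13.4 records adverse events from consent onwards.

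SAP 3.7.5 opens by having all adverse events coded in MedDRA and reported by SOC and preferred term. It then adds: "The focus of the adverse event summaries will be on treatment-emergent adverse events". The window is defined next: "Adverse events will be considered treatment-emergent if they occur on or after the start of the apheresis procedure, as defined in Section 3.2". The only matching statement in SAP 3.2 is this one: "A procedure will be considered to have been initiated if a Trima procedure start date and time are present". The sentences that follow in SAP 3.7.5, on frequencies, maximum severity, relationship and discontinuation, speak of AEs without naming a window.

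On the sequence of the apheresis day, Protocol 10.2.2 lists "1. Venipuncture" as its first step, "3. Update Trima Accel device with updated platelet count and hemoglobin or hematocrit" as its third, and the collection itself as step 4.

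**The concern.** The SAP can be read as narrower than the protocol. If the main tables were run only on events from the Trima start time, and that time were logged after the needle went in, an event that began at the needle stick would be classed as before treatment and left out of them.

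The protocol's own text makes the needle stick look relevant. Section 13.1.1 states: "Small hematomas, presyncopal episodes, and citrate reactions account for the majority of complications in automated collection procedures". Hematomas and presyncope can plausibly begin at venipuncture. Section 9.4 also treats venipuncture as the point of commitment, because "subjects who do not complete their anticipated procedure (after venipuncture) will be considered as an early termination". At stake is the completeness of descriptive safety tables: the report might understate common mild reactions and fall short of the protocol's all-event table. The primary and secondary endpoints are not involved.

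**Working it through.** The plan gives no figure to reproduce here. The check compares the texts and then looks at scale.

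**1. Does the SAP drop the all-event table?**
- Protocol 15.2.3: all AEs, SAEs and UADEs, safety population, frequency and percentage.
- SAP 3.7.5, opening sentence: all adverse events, by SOC and preferred term.
- SAP 3.7.5, after the window is defined: AEs, SAEs and UADEs with frequencies and percentages, no window stated.
- SAP 3.2: the Safety Population is used for all summaries except the two endpoints and the derived apheresis parameters.

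The last three together deliver the first. The sentence about focus sets emphasis; nothing in the SAP confines the summaries to treatment-emergent events. What is missing is a label on each table saying which window it uses.

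**2. Do the documents put the Trima timestamp after the needle stick?**
No. The step order in Protocol 10.2.2 hints at it, but step 3 is an update of the count. Protocol 15.4, item 3, compares a count already entered with one measured on a sample from the Trima disposable's own pouch. The machine and its set may therefore be in use before step 3. That does not prove the start time precedes the needle, but the step list cannot show that it follows.

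**3. How many donors could be involved?**
Inputs: an assumed 279 donors in the Safety Population (3 × 93), and the band of 1% to under 10% in Protocol Table 13-1 for hematoma or pain.

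Donors with a given event type = N × rate: 279 × 0.01 = 2.8; 279 × 0.10 = 27.9.

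Donors outside the window = that total × the share with onset before the timestamp. The documents give no share, so these are illustrations:

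| Assumed share | Donors outside the window | Percentage points of 279 |
|---|---|---|
| 0% | 0 | 0 |
| 10% | 0.28 to under 2.8 | 0.1 to under 1.0 |
| 50% | 1.4 to under 14 | 0.5 to under 5.0 |

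If all 450 donors allowed by SAP 3.1 started a procedure, the totals would be 4.5 to under 45; the percentage points would not change.

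For more serious reactions, Protocol 13.1.1 gives under 5 per 10,000 donations needing outside care, almost 40% of them related to venipuncture: 5/10,000 × 0.40 = 2/10,000, and 279 × 2/10,000 = 0.056 expected. The events in question are mostly mild.

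**4. Would starting the window at venipuncture be better?**
Protocol 10.2.2 does not list venipuncture time among the items to record. If it is not captured, the workable rule is to count every event on the apheresis date. Protocol 10.1 allows screening on that same day, so the rule could admit reactions to the screening needle, and Protocol 10.2.1 adds a finger stick. A possible undercount would be exchanged for a possible overcount.

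**The case for a change.** The strongest argument for a change does not depend on the timestamp. Donors new to a site without usable counts have a screening venipuncture up to 30 days earlier (Protocol 10.1). A reaction to that needle precedes the window wherever the Trima start falls, yet it is within the protocol's commitment if the donor later starts apheresis. Two programmers could also read SAP 3.7.5 differently, and the SAP has no rule for a same-day event without an onset time, while SAP 3.7 rules out imputation. A sentence or two would settle all of this.

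Part of this stands: the windows are unlabelled, and the status of the Day 1 needle stick is not stated. But screening reactions are lost only if the tables are limited to treatment-emergent events, and the SAP's opening sentence points the other way. An analyst holding both documents would produce one table of all events and one of treatment-emergent events. Tying the window to the same marker that admits a donor to the Safety Population is also coherent. SAP 3.7 lists all eCRF data, so no event disappears from the report. Listings do not replace the promised tables, but they would make any difference between the two visible.

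**Conclusion.** The concern does not call for a change. SAP 3.7.5 already provides for reporting all adverse events, in line with Protocol 15.2.3; the unstated window for each table is a detail that analysts settle in the table shells. Noting there whether the Day 1 venipuncture counts as part of the procedure would be helpful but optional.

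Loss of needle-placement events from the treatment-emergent tables requires the Trima start to follow the needle stick, which the documents do not establish. The loss could be zero. The illustrated upper end, under 14 of 279 donors for one event type, pairs the top of a frequency band with an unsourced 50% share. Following the plan as written is not shown to alter any primary, secondary or safety conclusion.

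This rests on reading the word focus as emphasis, and on the Safety Population being close to the 279 planned collections.

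### SAP disposition and safety tables are grouped by achieved platelet yield, so stopped or off-target collections can leave the column of the product that was attempted

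*SAP*

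**What the plan says.** SAP 3.2 fixes the grouping once for the whole plan: "For all analyses by platelet product, the platelet product type (single, double, triple, or unassigned) will be determined from the calculated platelet yield". A rounded yield of at least 9.3 (all yields here ×10^11) makes the product a triple. Failing that, at 6.2 or more "then the product will be analyzed as a double", and below 6.2 "then the product will be analyzed as a single", with no lower limit. The last bullet sends a record to Unassigned "if the procedure was not started, not completed or the platelet yield could not be determined for some other reason".

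The population for these tables is every initiated procedure: "The Safety Population will be used for all summaries except the primary and secondary endpoints and the derived apheresis related parameters". Two sets of tables then use the yield-based columns:

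- SAP 3.7.2: "Study completion status and reasons for discontinuation will be displayed by platelet products".
- SAP 3.7.5: "Summaries will be presented by platelet products (single, double, triple, and unassigned) and overall". The same section adds: "AEs leading to study or procedure discontinuation will also be tabulated".

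No table by attempted or selected product is specified.

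**The concern.** A column variable in a safety table should be settled before the events that it classifies. Here it is settled afterwards and partly by them. Protocol 13.2 has the procedure stopped when a moderate or severe AE occurs, and a stopped procedure has a low yield or none. The AE can therefore decide which column it is counted in.

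The tables most exposed are those of AEs leading to procedure discontinuation and of reasons for discontinuation. A reader will take a percentage in the triple column as the experience of donors who undertook a triple collection, but the column holds only collections that ended with a triple yield. What is at stake is the meaning of the by-product percentages in descriptive tables.

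**Working it through.** **No plan figure to reproduce.** The SAP gives no stop rate, AE rate or yield distribution by product. Its sample-size figures (93 products per type, with 1 or 16 allowed failures) concern the endpoints. The number 93 serves below only as a scale, because the safety columns are not limited to 93.

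**Step 1: apply the SAP 3.2 bullets to example collections.** Two readings are possible. On the natural reading, a procedure that was not completed is Unassigned. On the listed-order reading, the bullets run from top to bottom, so any measured yield is classified before completion is considered.

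| Selected product | Completed? | Yield | Natural reading | Listed order |
|---|---|---|---|---|
| Triple | Yes | 9.0 | Double | Double |
| Triple | Yes | 6.0 | Single | Single |
| Double | Yes | 6.0 | Single | Single |
| Double | Yes | 9.4 | Triple | Triple |
| Triple | No | 5.0 | Unassigned | Single |
| Double | No | 6.5 | Unassigned | Double |
| Double | No | None | Unassigned | Unassigned |

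Three things follow. Completed collections move on either reading, both down and up. Stopped collections always leave their column on the natural reading. On the listed-order reading, a stopped collection with a measured yield goes where that yield falls, and it stays in its own column if it had already passed its cut-point. Two programmers could therefore build different tables from the same data.

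**Step 2: size of the displacement on the natural reading.** Let s be the assumed share of triple attempts stopped for an AE. Stopped triples per 93 completed = 93 × s / (1 − s).

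- s = 0.1%: 93 × 0.001 / 0.999 = 0.09
- s = 1%: 93 × 0.01 / 0.99 = 0.9
- s = 5%: 93 × 0.05 / 0.95 = 4.9
- s = 10%: 93 × 0.10 / 0.90 = 10.3

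The triple column shows 0 AE-stopped procedures in every case. The range of s is an assumption. Protocol Table 13-2 gives context only: its bands (uncommon 0.1% to <1%, common 1% to <10%) are general apheresis event frequencies, not stop rates. The 10% value is an outer limit, since Protocol 13.1.3 says that most complications are mild.

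**Step 3: illustration with low-yield completions added.** Take 100 triples started, assume that 3% to 10% are stopped, and assume that 5% to 25% of the rest fall below 9.3. The number left in the triple column runs from 100 × 0.97 × 0.95 = 92 down to 100 × 0.90 × 0.75 = 67.5. If AEs occur in 10% of completed and 60% of stopped procedures (also assumed), the rate for all triples started is 0.10 × (1 − s) + 0.60 × s. That is 11.5% at s = 3% and 15% at s = 10%. The triple column would show 10%.

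**Step 4: is a pre-collection product available in principle?** Protocol 8.1 says that the device works out which product combinations a donor is eligible for. Protocol 10.2.2 has the counts updated on the device before the apheresis is performed. Protocol 10.3 speaks of a subject qualifying for a particular procedure. A product is thus identifiable before collection. No section names a recorded field for it; Protocol 10.2.2 lists only *Trima procedure details*, without contents.

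**The case against.** The SAP does provide for stopped collections. Its wording treats non-completion as one reason for lacking a yield, so Unassigned is their intended place. They stay visible there, in the overall column and in the listings, which SAP 3.7 says will present all eCRF data. Protocol 15.2.3 does not ask for AE tables by product, no between-product safety comparison is planned, and there is no safety acceptance rule. Matching the safety columns to the endpoint columns is a defensible choice. All of this stands, and it limits the weight of the point. It does not remove it: the SAP chose to tabulate discontinuations by product, and on its own rule those columns cannot show them. Unassigned does not repair this, because it mixes the three products and its denominator is not the number of attempts.

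Three stronger inferences are tempting but unsupported.

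- **That stopped doubles and triples would inflate the single column by a calculable amount.** This needs the listed-order reading, and partial products that are weighed and counted and yield below 6.2. Nothing in the documents says that aborted collections are assayed, so no size can be given.
- **That every stopped collection leaves its column on any reading.** On the listed-order reading, one already past its cut-point stays.
- **That the SAP contradicts Protocol 9.4.** That section defines early termination as a disposition status. It does not define a table column, and a donor can be both an early termination and Unassigned.

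**Conclusion.** The point holds and is minor. The by-product columns in the disposition and safety tables reflect achieved yield, so their percentages are not rates per attempted product. On the natural reading, the single, double and triple columns contain structural zeros for AE-stopped procedures at any true rate. The bullet order is also ambiguous for a stopped collection with a measured yield.

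The number of records affected cannot be taken from the documents. The figures of 0.09 to 10.3 stopped triples per 93 completed rest entirely on assumed stop rates of 0.1% to 10%, and the low-yield and AE-rate figures are illustrations. If few procedures are stopped or off target, few records move.

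A reader might infer that safety events are lost. They are not: overall counts and listings keep them all. A reader might also infer that the yield-based rule is harmless for the endpoints because these tables feed no acceptance rule. This point neither examines nor clears the use of the same rule for the endpoint columns.

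**What to change.** 1. In SAP 3.2, apply the branch for procedures not completed, or without a determinable yield, before the yield branches. This removes the ambiguity and leaves the Full Analysis Set unchanged, because exclusions 1 and 4 already remove incomplete collections.
2. Present the SAP 3.7.2 and 3.7.5 tables by the product selected on the device after the day-of count update (or the last product selected if there was no update), or add such tables to the present ones. In them, use Unassigned only where no product was selected. This depends on the sponsor confirming that the selected product is held in *Trima procedure details*.
3. If it is not recorded, keep the present columns and add a footnote that they reflect achieved yield and that by-product discontinuation and AE percentages are not rates per attempted product.

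The cost is a change of SAP wording, some table reprogramming, and a note explaining why safety columns differ from the endpoint columns. No new data collection is needed.
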